8.3.2. Outcome definitions

There are three groups of outcomes of interest:

Maternal outcomes

• Maternal death during pregnancy and up to 42 days after delivery.

Pregnancy outcomes

- Live birth defined as an infant born alive.
- Spontaneous abortion (SAB) in clinically recognized pregnancies defined as foetal death or expulsion of products of conception prior to 20 weeks' gestation, or if gestational age is unknown, weighing less than 500g.
- Stillbirths defined as a foetal death occurring at 20 weeks' gestation or greater, or if gestational age is unknown, a foetus weighing 500 g or more.
- IAB defined as voluntary interruption of pregnancy, including pregnancy termination that occurs electively, to preserve maternal health, or due to foetal abnormalities.

Birth outcomes

- Prematurity defined as an infant born at gestational age <37 weeks.
- SGA defined as an infant born with a birth weight less than the 10th centile for the corresponding gestational age.
- LBW defined as an infant whose birth weight is <2500 g.
- Neonatal death defined as death of the infant within 28 days of birth.
- Major congenital malformation (MCM) defined according to EUROCAT criteria
- EUROCAT includes all major structural malformations and chromosomal malformations. Minor anomalies are excluded (as defined in Section 3.2 of the coding guide) and cases with more than one malformation type are only counted once for the calculation of overall malformation prevalence.

Maternal and infant follow up is proposed to 3 months after birth. Longer term follow-up is not proposed as there are no pre-clinical or clinical data to suggest a signal for developmental delay. Hence, it is impossible to determine an appropriate longer term follow up period which differs substantially according to the type of developmental adverse outcome of interest. As the majority of major malformations are detected at birth, a three month follow up period is deemed adequate to maximize capture of major malformations.

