Retrospective reports include subjects for whom the pregnancy outcome has already occurred. Retrospective reports can be biased toward the reporting of more unusual and severe cases and are less likely to be representative of the general population experience than exposures reported prior to knowledge of outcome. Although the exposure can be identified objectives through the UKOSS/INOSS systems, there is still the potential for bias to be introduced if there are delays in the women consenting and between exposure and consent there is additional knowledge of the outcome of the pregnancy. Where possible, the characteristics of prospective and retrospective reports will be compared to assess potential bias. If there is adequate evidence to support lack of bias these prospective and retrospective reports may be combined for analysis, but the initial analysis position will be for retrospective reports with reported MCMs and/or SABs will be reviewed to aid in detection of early signals and listed in registry reports.

Loss to Follow-up

For a prospective report of pregnancy where follow-up information on the pregnancy outcome (live birth, SAB, etc.) is never obtained or is unavailable, the pregnancy will be considered lost to follow-up. Subjects lost prior to pregnancy outcome will be tallied in the registry reports but not included in the statistical analyses.

Duplicate Registry Reports

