The primary population for analysis will include all prospective evaluable participants exposed to IV zanamivir that are not lost to follow-up (i.e., participants with appropriate outcome information that meet the minimum criteria for evaluation). Because early prenatal testing is so frequent, it may be difficult to achieve adequate numbers of pure prospectively identified pregnant women if all pregnancies with prior prenatal testing are excluded from the analysis. Therefore, the primary analysis will include pregnancies enrolled prior to birth outcome but after prenatal testing as well (see definitions of prospective reports).

Secondary analyses may consider additional exposure populations captured through deidentified data sources. For example, UKOSS has ethical approval to collect a minimum exposure and outcome dataset on women exposed to new influenza treatments (including IV zanamivir) with a waiver of informed consent. This will enable capture of some data on women who may be exposed to IV zanamivir during hospitalisation with complicated influenza, but do not consent to participate in this study with more complete data collection. The potential and approach for combined analyses of patient populations, dependent on availability of common variables, will be fully described in the Statistical Analysis Plan.

Exclusions for Analysis Purposes

Invalid registry reports and pregnancies deemed lost to follow-up will be excluded from the primary analysis. Initial analyses will consider prospective and retrospective reports separately unless there is adequate evidence to support lack of bias associated with the retrospective reports. If the anti-influenza treatment to which the woman was exposed cannot be ascertained, an unknown exposure cohort will be established and analysed separately.

Sequential Pregnancies

The number and outcome of sequential pregnancies (subsequent pregnancies within the same woman) will be noted and presented. Sequential pregnancies will be included in the analytic dataset.

Multiple Gestation Pregnancies

The number, type (e.g., twin, triplet), and outcome of multiple gestation pregnancies will be noted and presented. Multiple gestation pregnancies will be included in the analytic dataset. These will be counted as multiple outcomes when the denominator is infant births.

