8.7.1. Essential analysis

This registry is primarily descriptive and designed to detect potential safety signals, rather than test hypotheses. GlaxoSmithKline is specifically interested in reporting the prevalence estimates of maternal deaths, birth outcomes and pregnancy outcomes including preterm birth, LBW, SGA and MCMs among pregnancies exposed to IV zanamivir and descriptively comparing them to external comparators to determine whether there is a signal of substantial increased risk with the IV zanamivir exposed group.

Demographic and baseline characteristics will be summarized with simple descriptive statistics and data listings for the evaluable populations of pregnant women and pregnancy outcomes. Demographic and baseline characteristics will also be summarized for the population that is lost to follow-up and compared with the evaluable populations to assess potential differences. These data will be reviewed for potential confounding factors that could affect the interpretation of comparisons of registry outcome prevalence estimates with those of comparators. Further details will be provided in the statistical analysis plan (SAP).

Prevalence point estimates and 95% confidence intervals will be calculated using the binomial distribution for prevalence estimates of maternal deaths, birth outcomes (live births, SAB, IABs, stillbirths) among pregnant women exposed to IV zanamivir and the pregnancy outcomes of preterm birth, LBW and SGA among their live births as well as MCMs among their live births and foetal deaths. For each prevalence estimate, both 1-sided and 2-sided 95% confidence intervals will be calculated and reported. One-sided confidence intervals are appropriate as we are specifically interested in detecting outcome prevalence estimates greater than their respective reference prevalence, and 2-sided confidence intervals will provide further description of the accuracy of the estimates. Prevalence estimates will be reported overall and according to the trimester of IV zanamivir exposure.

The prevalence of maternal deaths and birth outcomes (live births, SABs, IABs, stillbirths) will be calculated as proportions with the number of IV zanamivir exposed pregnancies as the denominator.

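### Maternal death is estimated only in women whose pregnancy outcome is known, and sections 8.7 and 8.7.1 do not say consistently which lost pregnancies are in the denominators

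*Protocol*

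**What the plan says.** Section 8.7 (Loss to Follow-up) treats a prospective report as lost "where follow-up information on the pregnancy outcome (live birth, SAB, etc.) is never obtained or is unavailable". The mother's vital status plays no part in this definition. The consequence follows at once: "Subjects lost prior to pregnancy outcome will be tallied in the registry reports but not included in the statistical analyses".

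The rule is carried into the populations defined later in 8.7. Evaluable reports must not be lost, and the primary population is "all prospective evaluable participants exposed to IV zanamivir that are not lost to follow-up". Under Exclusions for Analysis Purposes the scope is narrower: "Invalid registry reports and pregnancies deemed lost to follow-up will be excluded from the primary analysis".

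Section 8.7.1 says that maternal deaths, live births, spontaneous abortions (SAB), induced abortions and stillbirths "will be calculated as proportions with the number of IV zanamivir exposed pregnancies as the denominator". It does not limit that number to evaluable pregnancies. The same section gives lost women one use: "Demographic and baseline characteristics will also be summarized for the population that is lost to follow-up and compared with the evaluable populations".

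Section 8.3.2 lists maternal outcomes apart from pregnancy outcomes and defines the maternal one as "Maternal death during pregnancy and up to 42 days after delivery".

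**The concern.** Whether a woman counts towards maternal death depends on a different variable, the outcome of her pregnancy. The two can be known separately. A woman may be known to have died, for example after transfer, while the pregnancy outcome is never retrieved. Another may be known to be alive at discharge or at a later contact, while her delivery is never traced. The rule discards both.

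The second kind of loss is unlikely to be random. All participants are hospitalised, so an outcome during the admission is on the treating hospital's record. A woman who goes home pregnant must be followed to delivery. A baseline comparison of lost and evaluable women describes the two groups, but it does not correct a selection that works through the timing of the outcome.

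Maternal death is the first outcome named in the objectives, and few events are to be expected among 100 to 150 exposures. One dropped death, or a shrunken denominator, moves the reported prevalence that is to be set against external comparators.

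**Working it through.** **Inputs.** From the protocol: the loss rule and populations (8.7), the denominator (8.7.1), the maternal-death definition (8.3.2) and the planned 100 to 150 exposures (8.9.1). Not in the protocol, so assumed: the fraction lost l (5, 10, 20%), the number of deaths (5 in 100 women), and k, the risk of death in lost women relative to followed women (0, 0.5, 1, 2).

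The plan has no figure of its own to reproduce on this point. Table 1 of section 8.5 does reproduce with an exact one-sided binomial test (at 100 live births 2.05, 2.07 and 3.90), but it concerns live-birth outcomes and is not in question here.

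**Step 1: who is in the maternal-death estimate.**

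| Woman | Under 8.7 as written | If vital status decided |
|---|---|---|
| Died, pregnancy outcome recorded | In, event | In, event |
| Died, pregnancy outcome never obtained | Out | In, event |
| Alive at last contact, pregnancy outcome never obtained | Out | In, no event up to last contact |
| Pregnancy outcome recorded, not traced to day 42 | In, no event | In, no event up to last contact, shown as incompletely followed |

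Rows 2 and 3 are the defect. Row 4 is its mirror image: a woman lost after delivery stays in the denominator although the 42-day window is incomplete.

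**Step 2: size of the bias.** Let p be the risk in followed women and kp the risk in lost women. The full-cohort risk is p[(1 - l) + lk]. The estimate after exclusion is p. Their ratio is

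ratio = 1 / [(1 - l) + lk]

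| k | l = 5% | l = 10% | l = 20% |
|---|---|---|---|
| 0 | 1.05 | 1.11 | 1.25 |
| 0.5 | 1.03 | 1.05 | 1.11 |
| 1 | 1.00 | 1.00 | 1.00 |
| 2 | 0.95 | 0.91 | 0.83 |

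**Step 3: in counts.** Take 100 exposed women, 5 deaths, 20 lost.

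- No death among the lost: 5/80 = 6.25% (95% CI 2.1 to 14.0) against 5/100 = 5.0% (1.6 to 11.3). The ratio is 1.25, a shift of 1.25 percentage points.
- Two of the five known deaths among the lost: 3/80 = 3.75% against 5/100 = 5.0%, a ratio of 0.75. Here k = (2/20)/(3/80) = 2.67, and 1/(0.80 + 0.20 x 2.67) = 0.75, which agrees with the formula.

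**Step 4: the wordings side by side.** Loss to Follow-up removes lost women from the statistical analyses without qualification. Exclusions for Analysis Purposes removes them from the primary analysis. Section 8.7.1 divides by exposed pregnancies without saying whether the lost are among them. With the first set of counts in step 3, one reading of 8.7.1 gives 5/80 and the other 5/100.

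**The case against.** The strongest reply is that 8.7.1 should be read within the populations that 8.7 has already defined. On that reading the denominator means evaluable exposed pregnancies, and keeping lost women as non-events would go against the explicit loss rule. This is a fair reading, and a reader who infers an outright contradiction goes too far. What stands is that the qualifier has to be supplied by the reader, and that the two statements of scope in 8.7 still differ.

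A reader might also infer that lost women vanish from every analysis. They do not: they are tallied, and their baseline data are summarised and compared.

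Nor does the protocol say that the lost are nearly all discharged survivors. That is plausible, but their later course is unknown. An opposing mechanism exists too. The primary analysis takes prospective reports, and data entry follows consent. A woman whose pregnancy ends before she consents becomes a retrospective report, and one who dies before consenting may not enter the consented cohort. Some early in-hospital events may therefore be missing from the primary analysis as well.

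It is tempting to carry the same inflation over to early pregnancy loss. The documents do not support that. SAB is "foetal death or expulsion of products of conception prior to 20 weeks' gestation", so women first exposed later cannot have one but remain in the denominator, which pulls the prevalence down. The net direction is not established.

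One could argue that the open-ended list in the loss definition lets maternal death count as an outcome, since the follow-up table in 8.6.2.1 groups it with the pregnancy outcomes. But 8.3.2 separates the two, and the definition names the pregnancy outcome only.

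Finally, the protocol plans record abstraction, consent to further contact and repeated queries, so loss may be low. A factor of 1.25 lies inside the confidence interval and well below the 2- to 4-fold increases the registry aims to detect. That limits the weight of the point. It does not justify a rule that can drop a known death.

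**Conclusion.** The point holds for maternal death and for the clarity of the denominators. By its own wording, section 8.7 ties the maternal-death estimate to a known pregnancy outcome, so it can discard a known death and does discard women known to be alive when last seen.

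If the lost women had no deaths, the overstatement is 1/(1 - l), or 1.05 to 1.25 for 5 to 20% loss. If they carried twice the risk, the estimate would be too low, at 0.95 to 0.83 of the full-cohort value. All loss rates, event counts and relative risks are assumptions. Upward bias is the likelier direction for maternal death but is not proven. The size alone would probably not create or hide a 2-fold signal, but the bias is systematic and more enrolment would not remove it.

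For SAB and other pregnancy loss, only the ambiguity of the denominator is shown, not a direction of bias. How to model pregnancy loss over gestation can be left to the SAP, which was not available here.

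**What to change.** 1. In 8.7, limit the loss rule to pregnancy and birth outcomes. Analyse maternal death in all prospectively enrolled women with known vital status, whether or not the pregnancy outcome is known, and never drop a known death. Record the date and status at last contact, and report how many women were not followed to day 42 after delivery. Counting a woman as a survivor on her last contact assumes that no later death was missed, so that number should stand beside the estimate.
2. In 8.7.1, state one denominator for each outcome and say whether lost pregnancies are in it. Align the Loss to Follow-up and Exclusions for Analysis Purposes paragraphs of 8.7 with it.
3. For SAB and other pregnancy loss, keep the simple proportion among evaluable pregnancies, which suits comparison with published proportions. Add a sensitivity analysis that either keeps lost women as non-events or censors them at the gestational age of last contact.

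The cost is protocol wording, one last-contact date and status field, one extra sensitivity analysis, and a maternal-death denominator that differs from the one for pregnancy outcomes and so needs a footnote in the tables.

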8.7.1. Essential analysis

This registry is primarily descriptive and designed to detect potential safety signals, rather than test hypotheses. GlaxoSmithKline is specifically interested in reporting the prevalence estimates of maternal deaths, birth outcomes and pregnancy outcomes including preterm birth, LBW, SGA and MCMs among pregnancies exposed to IV zanamivir and descriptively comparing them to external comparators to determine whether there is a signal of substantial increased risk with the IV zanamivir exposed group.

Demographic and baseline characteristics will be summarized with simple descriptive statistics and data listings for the evaluable populations of pregnant women and pregnancy outcomes. Demographic and baseline characteristics will also be summarized for the population that is lost to follow-up and compared with the evaluable populations to assess potential differences. These data will be reviewed for potential confounding factors that could affect the interpretation of comparisons of registry outcome prevalence estimates with those of comparators. Further details will be provided in the statistical analysis plan (SAP).

Prevalence point estimates and 95% confidence intervals will be calculated using the binomial distribution for prevalence estimates of maternal deaths, birth outcomes (live births, SAB, IABs, stillbirths) among pregnant women exposed to IV zanamivir and the pregnancy outcomes of preterm birth, LBW and SGA among their live births as well as MCMs among their live births and foetal deaths. For each prevalence estimate, both 1-sided and 2-sided 95% confidence intervals will be calculated and reported. One-sided confidence intervals are appropriate as we are specifically interested in detecting outcome prevalence estimates greater than their respective reference prevalence, and 2-sided confidence intervals will provide further description of the accuracy of the estimates. Prevalence estimates will be reported overall and according to the trimester of IV zanamivir exposure.

The prevalence of maternal deaths and birth outcomes (live births, SABs, IABs, stillbirths) will be calculated as proportions with the number of IV zanamivir exposed pregnancies as the denominator.

The prevalence of preterm births, SGA and LBW will be calculated as proportions, with the number of live births as the denominator. Because MCMs are often associated with preterm birth and LBW, sensitivity analyses will be performed excluding infants with MCMs from the numerator and denominator when prevalence estimates are determined for these outcomes.

Formulas for the calculation of prevalence of the primary outcomes are presented below:

Preterm birth prevalence =	Number of preterm live births Number of live births
SGA prevalence =	Number of SGA live births Number of live births
LBW prevalence =	Number of LBW live births Number of live births
MCM prevalence =	Number of live births and foetal losses occurring at ≥ 20 weeks gestation with MCM Number of live births (all) plus number of foetal losses with MCM

Due to inconsistent ascertainment of malformations in early foetal losses these are not included in analyses. Furthermore, a conservative approach is taken to only include foetal losses ≥ 20 weeks with MCMs, rather than all foetal losses, in the denominator. This will result in an over-estimation of risk.

Because most structural defects have their origins in the first trimester of pregnancy during the period of organogenesis, analyses of MCMs will be stratified by trimester of exposure, if applicable. The second trimester will start at 14 weeks gestation and the third trimester will start at 28 weeks gestation. The prevalence of combined MCMs reported to the registry will be calculated as a proportion with the number of MCMs in live births and foetal losses as the numerator and the number of all live births plus foetal losses with a MCM as the denominator. Pregnancy losses with reported MCMs occurring at or after 20 weeks' gestation will be included in the numerator of the estimate of risk for MCMs to increase sensitivity. The prevalence of combined MCMs in exposed cases will be compared with that reported to EUROCAT AND MACDP. Only cases meeting the EUROCAT criteria will be included in the primary analysis.

As EUROCAT includes chromosomal malformations and MACDP excludes chromosomal malformations, all malformations types will be collected through the registry and the appropriate comparisons will be made with and without chromosomal malformations. There will also be alignment of denominators around inclusion of foetal losses to ensure appropriate comparisons are being made between external reference groups and the registry. Pregnancies exposed to major teratogens (see Section 8.3.3) will be excluded from analyses.

If it is feasible, descriptive comparisons between the registry and an appropriate internal and/or external comparison group will be examined (see Section 8.2 for a description of potential reference groups).

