8.4. Data sources

The current UKOSS/INOSS reporters will serve as data reporters identifying exposures for the registry within the UKOSS and INOSS networks. The registry is strictly observational; the schedule of health care visits and encounters as well as all treatment regimens will be determined by the treating HCP. There will be no additional laboratory tests or assessments required as part of this registry. Only data noted as part of routine care will be collected. Maternal characteristics and outcome data will be provided by research staff, where accessible. To aid follow up, the mother will be asked to consent to medical record release and further contact to facilitate pregnancy and infant follow up.

Additionally, the teratologist/geneticist on the scientific advisory committee (SAC) will provide an opinion regarding the possible temporal association of the IV zanamivir

exposure to the development of any observed congenital malformations. If additional information is needed to aid in classification or temporality assessment, the teratologist will request additional information using a targeted follow up process. The SAC will meet periodically to review the data including a discussion of the MCM cases and their classification and temporality with the teratologist and to reach a consensus on the coding and classification of MCMs and other primary endpoints. Healthcare providers may also report de-identified data to the registry. This could include exposures and outcomes identified through anonymised healthcare electronic medical record data sources.

A summary of data that will be collected at specific time points and the source of data are provided in Section 8.6.2.1.

For critical data points, if there are outstanding questions, discrepancies between forms, or missing data, the appropriate reporter will be contacted for clarification. Up to three subsequent attempts, as necessary, will be made at regular intervals (e.g. every two weeks).

Exposure operational definition

At least one dose of IV zanamivir administered at any time during pregnancy will constitute exposure. If the anti-influenza medication to which the woman was exposed cannot be ascertained, an unknown exposure cohort will be established and -analysed separately. Given the short half-life of IV zanamivir (two hours) the start of the exposure window will be conception estimated as described below.

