8.7. Data analysis

The following approach shall be taken for outcome case management within the registry.

Prospective Registry Reports

The registry will encourage prospective registration, which is defined as registration of a pregnancy exposure prior to knowledge or perceived knowledge of the pregnancy outcome (e.g., structural defect or genetic abnormality noted on a prenatal test).

Prospective reports will be further defined as traditional prospective and pure prospective reports. Traditional prospective reports of pregnancy will include all women who enrol in the registry before the end of pregnancy (live birth, foetal loss, etc), regardless of knowledge of normal or abnormal prenatal test results. Pure prospective reports of pregnancy are a subset of traditional prospective reports and include those where (a) the enrolee did not know at the time of enrolment whether the foetus had adverse outcome such as a malformation, and (b) no prenatal testing was completed prior to enrolment. As the severity of influenza increases with trimester of pregnancy it is likely that most

exposure to IV zanamivir will occur after prenatal screening has occurred. Therefore, in primary analyses, traditional and pure prospective reports will be grouped together.

Data from HCPs that provide de-identified data on all exposed pregnancies in their network will fall into the category of prospective registry reports, as these reports provide objective data on every pregnancy exposure in the network, both positive and negative outcomes. Thus, they avoid the reporting bias inherent in retrospective reporting only after a negative outcome has been noted.

Retrospective Registry Reports

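### The overall spontaneous abortion and preterm birth proportions count women exposed or enrolled too late to have the event, so they are diluted relative to the external rates they are compared with

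*Protocol*

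**What the plan says.** Three parts of the protocol combine here.

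- **Who is exposed.** Section 8.4 sets no gestational limit: "At least one dose of IV zanamivir administered at any time during pregnancy will constitute exposure". Section 8.7 adds no at-risk restriction to the main analysis: "The primary population for analysis will include all prospective evaluable participants exposed to IV zanamivir that are not lost to follow-up".
- **When the events can happen.** Section 8.3.2 defines SAB as "foetal death or expulsion of products of conception prior to 20 weeks", and prematurity thus: "Prematurity defined as an infant born at gestational age <37 weeks".
- **What the events are divided by.** Section 8.7.1 says the prevalences of maternal death, live birth, SAB, induced abortion and stillbirth "will be calculated as proportions with the number of IV zanamivir exposed pregnancies as the denominator". For the birth outcomes it says: "The prevalence of preterm births, SGA and LBW will be calculated as proportions, with the number of live births as the denominator".

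On timing, section 8.7 reasons that influenza severity rises with trimester, so most "exposure to IV zanamivir will occur after prenatal screening has occurred". No distribution of gestational age at exposure is given.

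Section 8.7.1 plans estimates overall and by trimester of exposure, with cuts at 14 and 28 weeks. Section 8.7.2 lists gestational age at enrolment only as a possible subgroup.

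**The concern.** A woman first dosed at 30 weeks can never enter the SAB numerator, and a woman first dosed at 38 weeks can never enter the preterm numerator. Both still count below the line. The same holds for a woman dosed earlier but enrolled prospectively after the window has closed.

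Women who enter before the window closes have also already passed part of it. Someone enrolled at 16 weeks has gone 16 weeks without a loss, and a simple proportion treats her as if she had been observed from the start.

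Section 8.5 measures the effect as the ratio of registry prevalence to reference prevalence, and section 8.7.1 looks for prevalences above reference. Dilution pulls that ratio down. A low overall SAB prevalence could then be taken as reassurance when it reflects only late exposure. Section 8.9 does not list late entry among the limitations.

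Because section 8.7.1 fixes the denominators, this is not a detail left open for the SAP.

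**Working it through.** **Inputs from the protocol.** Preterm reference 7.6%, one-sided 5%, power 80%, binomial, N = 100 live births, detectable ratio 2.05 (section 8.5, Table 1). SAB window before 20 weeks and preterm window before 37 weeks (section 8.3.2).

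**Assumptions.** The share exposed after each window, and the SAB reference rate; the protocol states neither. SAB reference: 10%, with 5% and 15% as the range.

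**Step 1. Reproduce Table 1.** Take the smallest r with P(X ≥ r | N, p0) ≤ 0.05, then solve P(X ≥ r | N, p1) = 0.80. For N = 100 and p0 = 0.076, r = 13 (exact error rate 0.0398) and p1/p0 = 2.05, as stated. All 15 cells reproduce. The table treats every live birth as exposed in time to be preterm.

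**Step 2. Dilution formula.** If a share f is exposed after the window closes and contributes no events, then

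observed ratio = true ratio × (1 − f).

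**Step 3. Preterm birth, N = 100, true ratio 2.05 among women exposed before 37 weeks.** Undiluted prevalence is 0.076 × 2.05 = 0.1558.

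| f (assumed) | Observed prevalence | Observed ratio | Power, all live births | Power, restricted denominator |
|---|---|---|---|---|
| 0% | 0.1558 | 2.05 | 80% | 80% (n = 100) |
| 10% | 0.1402 | 1.85 | 66% | 76% (n = 90) |
| 20% | 0.1246 | 1.64 | 48% | 72% (n = 80) |

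At f = 20% the ratio needed among at-risk women for 80% power is 2.05 / 0.8 = 2.56.

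**Step 4. SAB, 100 exposed pregnancies, assumed reference 10%, true doubling among women exposed before 20 weeks.** The threshold is 16 or more events.

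| Share exposed at ≥20 weeks (assumed) | Observed ratio | Power, all exposed | Power, restricted denominator |
|---|---|---|---|
| 30% | 1.40 | 32% | 77% (n = 70) |
| 50% | 1.00 | 4% | 56% (n = 50) |
| 70% | 0.60 | <0.1% | 39% (n = 30) |

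The observed ratios do not depend on the reference rate. At references of 5% and 15%, with half exposed late, power is 3% and 4% for all exposed and 38% and 78% when restricted.

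**Step 5. Trimester strata.** First-trimester exposure ends before 20 weeks, so that SAB stratum contains nobody exposed too late, though delayed entry remains. The second trimester (14 to 27 weeks) mixes exposure before and after 20 weeks. The third (from 28 weeks) mixes 28 to 36 weeks with 37 weeks or later, so the preterm dilution persists inside it.

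The restricted powers in steps 3 and 4 do not allow for delayed entry among women still at risk.

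**The case against.** **Stratification is already planned.** The first-trimester SAB stratum is free of late-exposed women. With an assumed 10% reference and a 3-fold excess, an exact one-sided 5% test in 20 or 30 such women has about 76% or 84% power. This stands and limits the concern mainly to the pooled estimate. Delayed entry within the stratum and its unknown size remain.

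**For preterm birth the net direction is not established.** A reader might infer that both prevalences are biased low overall and would hide a signal. The documents do not support that for preterm birth. Section 6.1 cites a 4-fold preterm risk in infected mothers, and section 8.2 accepts that general-population comparators lack the same baseline risk. At 4 × 7.6% = 30.4% with 20% exposed at 37 weeks or later, registry prevalence is 30.4% × 0.8 = 24.3%, and the chance of reaching 13 of 100 exceeds 99%. Against that comparator a false signal is as much a risk as a missed one. The two biases have different causes and need not cancel.

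**The sizes rest on assumed timing.** This stands. If exposure were uniform over 38 weeks from conception, 3/38 ≈ 8% would fall at 37 weeks or later and preterm power would be 69%. It would also be too strong to say that SAB prevalence must fall below any background rate: with 70% exposed before 20 weeks, a 3-fold excess over 10% gives 21% and 92% detection.

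**SAB is not a sized outcome, and the registry is descriptive.** Table 1 omits SAB and no hypothesis test is planned. But SAB is a named outcome to be set against external rates, and a descriptive comparison still needs matching periods at risk. The denominator alignment in section 8.7.1 concerns foetal losses in the malformation comparison, not time at risk.

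**Conclusion.** The concern holds for the overall estimates. Section 8.7.1 includes pregnancies that cannot contribute the event, and nothing elsewhere in the protocol corrects it. The observed ratio is multiplied by the share exposed while still at risk, and delayed entry adds further downward bias.

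The pooled SAB estimate is the most exposed, since treatment is expected to come mostly after prenatal screening: under the half-late assumption a true doubling disappears. For preterm birth the denominator lowers the ratio by an amount that depends on unstated timing, while influenza acts in the opposite direction against general-population rates. The supported conclusion there is a distorted comparison of uncertain net sign. Table 1 is arithmetically right, but its preterm column holds only if every live birth was exposed before 37 weeks.

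**What to change.** - **SAB.** For external comparison, use pregnancies exposed and enrolled before 20+0 weeks. Estimate cumulative incidence with delayed entry at the later of exposure and enrolment, treating other ends of pregnancy as competing events.
- **Preterm birth.** Beside the all-live-births figure, report the prevalence in live births exposed and enrolled before 37+0 weeks, with a delayed-entry estimate by gestational age at entry. Restriction alone is not enough: a woman exposed at 36+5 weeks would stay in the denominator with almost no time at risk.
- **Study size.** State in section 8.5 that Table 1's preterm effect sizes assume every live birth was exposed before 37 weeks.
- **Existing proportions.** Keep the all-exposed proportions as descriptive.

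This is a change of wording in the protocol and SAP. Exposure date, enrolment date and EDD, CEDD or LMP are already collected. The price is smaller denominators and wider intervals, mainly for SAB.
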